6.2.2 Blinding

Blinding will be maintained throughout the study for all study participants and study personnel, except the pharmacists.

6.2.3 Unblinding

Unblinding before the study is completed will occur only if a participant's well-being is threatened and the investigator believes unblinding is necessary to protect the participant.

Before treatment assignment for an individual participant is unblinded, the investigator must confer with the study sponsor and the medical monitor. The site investigator will notify the protocol chairs of the unblinding event, and the medical monitor will notify the study management team (SMT).

The emergency unblinding will be recorded and reported to the DSMB. A full account of the event will be recorded, including the date and time of the emergency, the reason for the decision to unblind, and the names of the medical monitor and others who were notified of the emergency. During site visits, the site monitor must verify that the medical monitor was notified and that a written account was completed. The reasons for unblinding of a participant's treatment will be included in the final study report.

Sponsor approval is required for unblinding the treatment of an individual participant or subgroups of participants for unplanned interim analyses to support DSMB reviews and final analysis.

6.3 VISIT WINDOWS

6.3.1 Scheduled Visits

All scheduled study visits in Appendix 1 must occur within the time limits specified below. Visits that occur outside of the specified windows will be considered protocol deviations.

- **Visit -1** Up to 2-4 weeks before visit 0
- **Visit 0** No window
- **Visit 1** (\pm 3 days)
- **Visits 2-7** (\pm 7 days)
- **Visits 8-11** (\pm 14 days)

6.4 GENERAL ASSESSMENTS

- Medical history includes T1DM time of diagnosis and clinically significant diseases or medical procedures. Copies of growth velocity charts should be obtained if available
- Adverse events. Participants will be assessed for AEs
- Concomitant medications. All concomitant medications and their indications will be recorded
- Comprehensive physical examination and vital signs. Weight, temperature, blood pressure, respiration, and pulse

6.5 LABORATORY ASSESSMENTS

- Serum chemistries: Electrolytes (sodium, calcium, potassium, chloride, phosphate, total CO₂), blood urea nitrogen (BUN), creatinine, and liver panel (AST, ALT, alkaline phosphate, direct and total bilirubin)
- Hematology: Complete blood cell count with differential, and platelets
- Infectious disease serology, hepatitis B (HBsAg and anti-HBcAb) and C, HIV, toxoplasmosis, VZV, EBV (IgG, IgM, EBNA), CMV (IgG, IgM)
- PPD skin test or IGRA
- Urine hCG
- Urinalysis
- C-peptide levels (measured as part of MMTT)
- Plasma Glucose (measured as part of MMTT)
- HbA_{1c} levels

6.6 DISEASE-SPECIFIC ASSESSMENTS

- MMTT
- Glucose (glucometer readings)
- Insulin use (U/kg body weight/day)
- Hypoglycemia events
- Serum Adiponectin levels
- Plasma Glucagon levels
- Plasma Proinsulin levels

6.7 BONE AND MINERAL METABOLISM ASSESSMENTS

Serum calcium, serum phosphate, PTH, 25-OH Vitamin D and serum bone turnover markers (serum CTX, osteocalcin). Bone turnover markers are exploratory only and are not part of the secondary endpoint safety assessment, per section 3.3.2.

6.8 GROWTH RATE ASSESSMENTS FOR GROWING-AGE PARTICIPANTS (AS DEFINED IN SECTION 5.2.9)

- Plain radiograph of left hand to determine bone age using the FELS atlas (Assessing the skeletal maturity of the hand-wrist).¹⁷⁹
- Height measured by Stadiometer.
- Secondary sexual characteristics.
- Arm span.
- Biochemical assessments. IGF-1, IGF-BP3, LH, FSH, estradiol (females), testosterone (males), TSH, and tissue transglutaminase.

7. MECHANISTIC ASSAYS

The study team will partner with the ITN for mechanistic studies, taking full advantage of their systems for sample collection and archiving (see letter from [name]). Following results of the study, various immunological assays will be considered through the available ITN cores, and beyond. We recognize that this field is rapidly evolving, and thus novel assays that are particularly relevant to this study population, and to this drug, will be considered. Our mechanistic assays plan is outlined below.

7.1 RATIONALE

The rationale for treating T1DM patients with imatinib stems from results in animal studies where imatinib therapy led not only to reversal of T1DM but also to reversal of the loss of tolerance, a process ultimately responsible for the pathology of the disease.

Treatment with imatinib potentially leads to a change from a pro-inflammatory to an anti-inflammatory state. In the NOD mouse model it was shown that both adaptive immune and inflammatory mechanisms directly trigger insulinitis, insulin resistance, faulty insulin signaling and islet cell destruction, all leading to the loss of tolerance to islets.

It is anticipated that drug treatment is likely to affect T cells, B cells and mast cells directly, resulting in decreased numbers and function of islet antigen-specific T cells and perhaps changes in autoantibodies. In T1DM, there is a growing belief that generalized inflammation and adaptive immunity are major contributing factors to the induction and progression of this autoimmune process. Thus, a decrease in these cells or their function might help to eliminate activated autoreactive T cells resulting in tolerance to islet antigens in T1DM patients. In addition, we hypothesize that imatinib alters PDGF signaling that alters macrophage differentiation, affecting the balance of pathogenic versus alternatively activated macrophages and inflamed endothelial cells altering cell trafficking.

The goal of the mechanistic studies will be to determine if the biological effects of imatinib correlate with therapeutic efficacy in T1DM patients. The proposed immunologic mechanistic studies are designed to determine how imatinib therapy may arrest ongoing autoimmune pancreatic β -cell destruction and preserve insulin secretion in patients with T1DM. These will be conducted in the existing Immune Tolerance Network core laboratories. We recognize that this field is rapidly evolving, and thus novel assays that are particularly relevant to this population and this agent may be incorporated into the trial at a later date. Whenever possible, samples will be frozen and archived for batch analysis at a later date. Finally, since this trial has a safety component, emphasis will be placed on the study of immune responses to pathogens and overall immune competence.

7.2 RETENTION OF SAMPLES

Biological specimens collected in this trial may be used to re-evaluate biologic responses as new research tools become available. The specimens will be stored at the ITN sample repository until the end of the ITN contract. Residual specimens may be used by the investigators for development of new immunologic assays or for cross-trial comparisons. Specimens for mechanistic studies will be obtained throughout the study. While specimens are described in this protocol in the context of assays to be performed, it should be noted that not necessarily all assays will be performed for all participants at each time point. Decisions to perform assays will be made according to statistical and scientific planning, questions being asked, and current technologies to be utilized. Finally, clinical outcomes will be taken into account to determine the potential value of the assays. For example, if a clinical effect fails to occur, the assays performed by the ITN may be minimal.

7.3 FROZEN PBMCs

Peripheral blood will be collected at the sites, processed at an ITN core laboratory, and frozen cells stored in a central ITN repository.

7.3.1 Functional Cell-Based Assays

The functional status of lymphocyte subsets, specifically T/ B cells, mast cells and monocytes, can be assessed in various cell-based assays. Inflammatory and TCR-driven autoantigen-specific stimulations need to be examined to fully evaluate the effect of imatinib on immunological responses. To address the participants' overall inflammatory response potential during imatinib treatment, PBMCs or whole blood can be stimulated with anti-CD3 plus anti-CD28 and/or lipopolysaccharide (LPS) to determine the array of secreted cytokines and chemokines made by T and B cells, respectively. Since inflammatory cytokines direct the commitment of antigen-activated CD4 T cells to specific effector or FoxP3 regulatory cells, the overall pattern of secreted cytokines might indicate a preference towards specific CD4 T-cell commitment. T-cell assessments will include those measuring both the number and function of T cells. These measures may include the use of class I and class II tetramers to enumerate antigen-specific T cells. Additionally, *in vitro* cell culture techniques may be utilized to study T cell functionality. Readouts will include ELISPOT and intracellular staining technology for cytokine determination. Additional studies may be done to study regulatory T cells in these treated participants. Both carboxyfluorescein diacetate succinimidyl ester (CFSE) and ³[H]-thymidine assays could be employed depending on cell numbers. Harvested blood cells will be separated by flow-based sorting using CD4, CD25 and CD127 antibodies and assayed for their ability to suppress polyclonal T cell responses. Follow-up experiments can include examination of Treg cell function as well as Foxp3 methylation. Several assays can address responses to autoantigens implicated in T1DM. Secretion of various cytokines can be determined, thus enabling characterization of overall phenotype (Th1/Th17/Th2/Treg) of T-cell responses, which might indicate skewing towards a more regulatory phenotype during imatinib treatment.

Imatinib can alter the differentiation of human and mouse DCs into mature APCs. The treated cells could not be induced to mature with IFN γ or CD40 agonists and were unable to stimulate T cells. In fact, the DCs look very much like the "tolerogenic" DCs defined in a number of settings. Other cell types may be analyzed that have been shown to play important roles in diabetes development and progression. These include B cells, NK cells, NKT cells and macrophages. We may perform functional analyses of these cells during and after therapy.

PBMCs will be isolated from blood, frozen by established ITN protocols, and studied in batches for quality control and standardization. These assays will be used in an attempt to test the hypothesis that imatinib treatment in humans, as in the NOD model, will tip the balance of inflammation toward an anti-inflammatory state, thus triggering

beneficial changes in T cell-directed autoimmunity.

7.3.2 FLOW CYTOMETRY PANEL STAINING

It is essential that we examine both *in vivo* and *in vitro* the effects of imatinib on DC maturation and function. The ITN core will perform multi-parameter flow cytometry on frozen cells. Changes in the following sub-sets of cells during treatment may be analyzed using various cell surface markers: B-cells (IgM, CD21, CD23, MHC class II, B7, etc); NK and NKT cells; macrophages, and mast cells. Myeloid DC and lymphoid DC-specific markers may also be examined to determine if DC number and subsets are altered. In addition, expression of activation markers MHC class II, CD40 and CD80, and CD86 molecules may be assessed to determine the state of DC maturation. Of special interest would be examination of various T cell subsets based on phosphoprotein and transcription factor expression, after activation. Flow cytometric evaluations of T cell and antigen-presenting cell subsets might complement the functional studies, enabling a better understanding of adaptive and innate immune compartments. Flow cytometric evaluations may also include the use of class I tetramers for detection of CD8 T cells implicated in the pathogenesis of T1DM. Specifically, HLA-A2 tetramers that enable detection of CD8 cells specific for the following antigenic peptides could be used: GAD 65 114-123, preproinsulin 2-10, IGRP 228-236, insulin B chain 10-18, and insulin A chain 1-10. As shown in preliminary studies, these cells can be visualized directly *ex vivo* without a need for *in vitro* auto-antigen induced expansion. When possible other validated class I tetramers may be included as they become available that utilize other autoantigen specificities and HLA restriction elements. Alternatively, other tools for visualization of autoantigen specific T cells might be used, such as engineered antibodies containing dimeric MHC/peptide complexes or other MHC/peptide multimers. Finally, we will work with Drs. [name] and [name] in Denver to use newly developed class II MHC tetramers that take advantage of mutations that fix autoantigenic peptides in specific registers to maximize TCR binding. Identification of autoantigen-specific CD4 or CD8 T cells directly *ex vivo* would provide a unique opportunity to reveal the function of these cells without manipulation. In combination with *ex vivo* polyclonal activation with agents like 4-phorbol 12-myristate 13-acetate (PMA) and ionomycin, it would be possible to also address the cytokine production profile of these cells along with expression of co-stimulatory and activation molecules.

7.3.3 GENOMICS AND PROTEOMICS

Imatinib has been shown to have several downstream targets. For instance, imatinib treatment of DCs resulted in decreased activation-induced upregulation of nuclear-localized RelB, RelA, c-Rel, NFkB, p50 and reduced phosphorylation of AKT, suggesting that imatinib mediates its effects in part via the NFkB pathway (AKT is upstream of NFkB). A reduction of NFkB and phosphorylation of Lck and ERK1/2 were observed in PHA-stimulated T cells treated with imatinib. These biochemical results suggest a series of pathways to be investigated in cells isolated from treated

individuals. We may analyze the biochemical effect of imatinib in T, B and dendritic cells, including the examination of the global effect of imatinib on tyrosine phosphorylation in T cells *in vitro* and in cells recovered from imatinib-treated patients. Studies will be designed to determine if imatinib affects phosphorylation of TCR, ZAP-70 and LAT equally, differentially or not. More precise studies on important protein kinases in the TCR signaling pathway, notably ZAP-70, ERK1/2 and AKT, could be performed by immunoprecipitation followed by western blotting in order to track their phosphorylation state (intra-cellular phospho-flow cytometry may also be used). The active form of c-abl may also be assessed in these cells. Similar studies will be performed in B cells if data suggests that B cells are a major target for imatinib activity in T1DM. The ITN may also examine the effect of imatinib treatment on DCs. Purified splenic CD11c⁺ DCs could be cultured with LPS or CD40L and in the presence or absence of imatinib for 24 hours, then nuclear extracts prepared to assess translocation of NFkB.

7.4 SERUM ASSAYS

7.4.1 SERUM-AUTOANTIBODY ANALYSES

Key markers for the presence of the autoimmune processes directed against pancreatic islets include assessing the presence and titers of anti-GAD65, anti-insulin, anti-ICA512/IA-2, and anti-ICA autoantibodies. Detection of these autoantibody combinations has proven to be an accurate predictor of T1DM in several natural history studies. In the DPT-1 prevention study, over half of the individuals who were positive for two of these antibodies progressed to full disease. Shifts in the titers of Ig isotypes may indicate a change in the type of T-helper cell responses to autoantigen. For example, increases in titers of anti-GAD IgE, IgG2, or IgG4 antibodies could indicate a shift to a more regulatory-type cytokine profile following drug administration. In summary, this study will test the hypothesis that successful treatment will be associated with a reduction in the titer or isotype of diabetes-related autoantibodies.

7.4.2 SERUM ARCHIVE

Patient serum will be archived for future studies. These studies might include measurements of cytokines and subsequent correlation with induction of clinical tolerance. The archived plasma samples could potentially be used for analysis of immune and inflammatory molecules at the proteosome and transcriptosome levels. In addition, expression of pro-inflammatory cytokines (PDGF, IL-1 β , IL-6, IL-12, TNF α), molecules that are induced by inflammation (SOCS1, 2, 3 and acute phase reactants, e.g., ceruloplasmin, SAA, CRP), and anti-inflammatory cytokines (TGF- β , IL-10) could also be assessed to determine the effect of imatinib treatment. We anticipate that novel assays relating to beta cell death may also be run from archived samples using differentially methylated circulating DNA¹⁸⁰.

7.5 WHOLE BLOOD-GENE-EXPRESSION PROFILING

To further elucidate possible changes in cytokine and cellular profiles, gene-expression profiling analysis may be performed on RNA isolated from peripheral blood using microarray or high-throughput real-time polymerase chain reaction (RT-PCR). RT-PCR can be used to compare the expression of several genes reported to play a role in T1DM, which might include IFN γ , TGF β , IL-4, Tbet, ROR γ t, FOXP3, STAT molecules, IL-2, IL-5, IL-13, IL-15, IL-21, IL-23 and IL-25. The goal of these assays is to identify differences between a tolerant versus non-tolerant state and to find new genes that could serve as potential markers of disease. These types of analyses may also explain why some individuals respond better to this treatment or elucidate mechanisms resulting in adverse responses to treatment. This assay has proven informative in characterizing unique genes that determine the clinical course in systemic lupus erythematosus, and preliminary studies with this technology have enabled us to determine a distinct subset of genes that are either up- or down-regulated in those with new-onset T1DM as opposed to controls in other studies.

7.6 WHOLE BLOOD DNA-HLA GENOTYPES

DNA collected from participants will be used to perform sequence-based HLA typing. A complete class I and class II haplotype will be performed, including fine typing of the DQB and DRB regions. Genotyping for single nucleotide polymorphisms (SNPs) in selected immune-response genes may also be performed. The results of genotype analyses might be used to correlate with disease progression and therapeutic responses (tolerance induction). In addition, collected DNA may be used for epigenetic analysis that includes histone modification and DNA methylation studies.

7.7 CHANGE IN BETA CELL FUNCTION

Many of the measures that we will utilize in assessing changes in beta cell function are now standard assessments in new-onset T1DM trials (see Section 3.3). However, these studies have ignored changes in insulin sensitivity. Imatinib may have novel effects on beta cell function and insulin sensitivity, as noted by the pre-clinical studies and effects in subjects with type 2 diabetes. We recognize that euglycemic hyperinsulinemic clamps are the gold standard for assessment of insulin sensitivity, but pose significant additional subject and investigative team burden and expense. We will assess changes in adiponectin levels in study patients, as these have shown dramatic increases in patients with type 2 DM on imatinib¹²⁶. We will also use data derived from MMTTs to model beta cell function and insulin sensitivity, as has been employed by others^{181,182}(see letter of collaboration from [name]). In addition to glucose and c-peptide levels, plasma glucagon, and proinsulin levels will be measured to further explore the effects of Imatinib on insulin sensitivity.

8. ADVERSE EVENTS

8.1 ADVERSE EVENT DEFINITION

8.1.1 Adverse Event

In this clinical trial, an adverse event is any occurrence or worsening of an undesirable or unintended sign, symptom or disease whether or not associated with the treatment and study procedures.

Throughout the study, the investigator must record all adverse events on source documents. Events not related to hypo or hyperglycemia that are Grade 2 or greater per the NCI CTCAE 4.0 (see Section 8.1.4. Grading Event Severity below) must be reported to the Coordinating Center on the appropriate adverse event form. The investigator should treat participants with adverse events appropriately and observe them at suitable intervals until the events resolve or stabilize.

Adverse events may be discovered through:

- observation of the participant;
- questioning the participant;
- unsolicited complaint by the participant

In questioning the participant the questioning should be conducted in an objective manner.

An abnormal value or result from a clinical or laboratory evaluation (e.g., a radiograph, an ultrasound, or an electrocardiogram) can also indicate an AE if it is determined by the investigator to be clinically significant. If this is the case, it must be recorded in the source document and as an AE on the appropriate AE form(s). The evaluation that produced the value or result should be repeated until that value or result returns to normal or can be explained and the participant's safety is not at risk.

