Liver toxicity, if an issue, usually emerges during the first few months of therapy, but can be a late finding. Frequent monitoring of liver function is suggested during therapy. Grade 1 elevations in transaminases occur in up to 10% of treated patients and often normalize while continuing on therapy. Grade 3 events have been reported in 2%–5% of subjects in GIST and CML trials, but these events may be confounded by a variety of other factors, including leukemic liver infiltration. For grade 3 events in oncology settings, therapy is temporarily interrupted. Imatinib is permanently discontinued for grade 3 events that recur with drug re-challenge.

1.5.1.7 *Myelosuppression*

The development of myelosuppression is much more common in CML than GIST, and may relate to the underlying effects of the cancer on the bone marrow. In the phase II study of imatinib for GIST, anemia (9% of subjects, 2% grades 3 or 4), neutropenia (7% of subjects, 5% grade 3 or 4), and leukopenia (5% of subjects, 1% grades 3 or 4) were the most commonly reported findings; grades 3 or 4 thrombocytopenia was noted in <1%. Complete blood counts with differential will be monitored at the same time points as liver function tests. For myelosuppression of grade 3 or higher severity in oncology

settings, therapy is temporarily interrupted, and permanently discontinued for grade 3 events that recur with drug re-challenge.

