3.3.2 Secondary Endpoints

Efficacy:

1. MMTT-stimulated peak and 4 hour C-peptide AUC at weeks 52 and 104.
2. MMTT-stimulated 2 hour C-peptide AUC at week 104.
3. MMTT-stimulated 2-hour C-peptide AUC assessed longitudinally at weeks -2, 13, 26, 52, 78, and 104.
4. Insulin use in units per kilogram body weight per day at weeks 52 and 104.
5. Major hypoglycemic events, as defined in section 8.2.1, occurring from randomization at weeks 0, 52 and 104.
6. HbA1c levels at weeks 52 and 104.

Safety:

The rate of the following AEs in participants receiving imatinib or placebo:

1. Myelosuppression.
2. Gastrointestinal disorders.
3. Infections.
4. Hepatotoxicity.
5. Cardiac toxicity and edema.
6. Cutaneous reactions.
7. Muscle cramps, bone pain, arthralgias.
8. Fluid retention or peripheral edema.
9. Bone metabolism and growth abnormalities
10. Frequency and severity of all AEs in participants receiving imatinib or placebo.

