5.2.5 Hepatotoxicity

In general, guidelines established for imatinib use in CML and GIST will be followed,^{129,130} but a more conservative approach will be used, as follows. Liver function tests (LFTs) will be obtained every other week during the first month of therapy, and monthly thereafter.

For grade-2 transaminase (ALT or AST $> 3.0 \times \text{ULN}$) or bilirubin ($> 1.5 \times \text{ULN}$) elevations, imatinib must be suspended, and the LFTs monitored weekly. When they have fallen to grade 1 or normalized, imatinib will be restarted at 50% of the initial daily dose. If the liver toxicity does not recur within 6–12 weeks, then the initial dose will be restored. If after resumption of treatment grade 2 transaminase or bilirubin elevations recur, study drug will be permanently discontinued.

For grade-1 abnormalities (ALT or AST greater than or equal to $1.0\text{--}3.0 \times \text{ULN}$; bilirubin greater than or equal to $1.0\text{--}1.5 \times \text{ULN}$), imatinib treatment can be continued but LFTs will be monitored weekly for 2 weeks and then, if no worsening is observed, every other week. Concomitant hepatotoxic agents, such as alcohol or acetaminophen, should be removed. Persisting grade 1 abnormalities should be managed by dose reduction, biweekly monitoring, and further evaluation in conjunction with gastroenterology consultation.

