8.2 ADVERSE EVENT REPORTING AND MONITORING

Study personnel will assess adverse events and the use of concomitant medications throughout the study. Adverse events will be reported to the Coordinating Center as described below. They will be graded as to severity according to common toxicity criteria or study-specific criteria and the investigator will make a determination as to the relation to therapy. Events will be assessed and reported in accordance with the ICH Guideline For Good Clinical Practice and per the guidance of the DHHS Office for Human Research Protections (OHRP). The adverse event case report form for the protocol must be completed for all adverse events (AE) of Grade 2 or greater severity regardless of relationship to therapy. For reporting serious adverse events (SAE), the MedWatch Form should also be completed and faxed to the Coordinating Center *within 24 hours of when the site was notified of the event*. This will be reviewed by the study Safety Monitoring Committee, and the Data and Safety Monitoring Board (DSMB) as appropriate. Deaths must be reported immediately. Event outcome and other follow-up information regarding the treatment and resolution of the event will be obtained and reported when available, if not known at the time the event is reported. The follow-up information should contain sufficient detail to allow for a complete medical assessment of the case and an independent determination of possible causality.

Adverse events will be assessed by the study designated Medical Monitor. The DSMB will conduct regular safety reviews approximately every three to six months (and, as needed) of adverse events by treatment group assignment. Serious adverse events as well as adverse events leading to treatment discontinuation will be reviewed by the DSMB.

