Appendix 1. Schedule of Events

Week	-3 to -4	0	2	4	9	13	17	22	26	39	52	78	104
Visit	-1	0	1	2	3	4	5	6	7	8	9	10	11
GENERAL ASSESSMENTS													
Informed consent	X												
Eligibility criteria	X												
Medical history	X												
Adverse events	X	X	X	X	X	X	X	X	X	X	X	X	X
Concomitant medications	X	X	X	X	X	X	X	X	X	X	X	X	X
Physical examination ¹	X	X		X	X	X			X		X	X	X
Secondary sexual characteristics ²		X									(X)		(X)
Vital Signs	X	X	X	X	X	X	X	X	X	X	X	X	X
Pregnancy Monitoring (if applicable)	X	X		X	X	X	X	X	X		X	X	X
ECG	X		X										
LABORATORY ASSESSMENTS													
Serum chemistries and liver panel ³	X	X	X	X	X	X	X	X	X	X	X	X	X
Autoantibodies	X												
Hematology ⁴	X	X	X	X	X	X	X	X	X	X	X	X	X
Infectious disease serology ⁵	X												
PPD skin test or IGRA	X												
Urine hCG	X	X		X	X	X	X	X	X		X	X	X
Urinalysis	X								X		X		X
Prostate Specific Antigen (males only)		X							X		X		X
C-peptide levels (tested from MMTT) ⁶	X					X			X		X	X	X

¹Excluding genitalia unless clinically indicated

² The Tanner stages will be assessed at the baseline visit for every participant under 18 years of age. After the baseline visit, Tanner stages will be assessed annually on all participants who are < stage 3. If the Tanner stage is ≥ 3 at the baseline visit or any subsequent visit, Tanner stages will not need to be assessed at any future visit.

³ To include sodium, calcium, potassium, chloride, phosphate, total CO₂, BUN, creatinine, AST, ALT, alkaline phosphate, direct and total bilirubin.

⁴ Performed locally; to include CBC with differential and platelets.

⁵ Hepatitis B and C, HIV, toxoplasmosis, VZV, EBV, and CMV serology. CMV/EBV PCR testing may be obtained (centrally) or locally, if necessary to confirm active infection.

⁶ 4-hour MMTT at Visits -1, 9, 11 and 2-hour MMTT at Visits 4, 7, and 10.

Week	-3 to -4	0	2	4	9	13	17	22	26	39	52	78	104
Visit	-1	0	1	2	3	4	5	6	7	8	9	10	11
Plasma Glucose (tested from MMTT) ⁵	X					X			X		X	X	X
HbA _{1c} levels	X					X			X	X	X	X	X
STUDY DRUG ADMINISTRATION													
Study drug administration		X	X	X	X	X	X	X	X				
Study drug compliance			X	X	X	X	X	X	X				
DISEASE SPECIFIC ASSESSMENTS													
Glucose (Glucometer Reading)		X	X	X	X	X	X	X	X	X	X	X	X
Insulin use		X	X	X	X	X	X	X	X	X	X	X	X
Hypoglycemia assessment		X	X	X	X	X	X	X	X	X	X	X	X
Serum-Adiponectin ⁷		X		X					X		X		X
Plasma-Glucagon ⁶	X					X			X		X	X	X
Plasma-Proinsulin ⁶	X					X			X		X	X	X
BONE AND MINERAL METABOLISM													

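### Myelosuppression and hepatotoxicity are endpoints only as AE rates, and the only stated route by which a symptomless laboratory abnormality becomes an AE is investigator judgement; graded laboratory tables should be added.

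*Combined protocol and SAP*

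**What the plan says.** Section 3.3.2 introduces the safety endpoints as "The rate of the following AEs in participants receiving imatinib or placebo". Myelosuppression is item 1 and hepatotoxicity is item 4. Neither has a laboratory threshold.

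Section 8.1.1 says that "an adverse event is any occurrence or worsening of an undesirable or unintended sign, symptom or disease", and then that an abnormal laboratory result "can also indicate an AE if it is determined by the investigator to be clinically significant". The routes of discovery it lists are observing the participant, questioning, and unsolicited complaint.

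The reporting rule covers "Events not related to hypo or hyperglycemia that are Grade 2 or greater per the NCI CTCAE 4.0" (8.1.1). Section 8.2 repeats that the AE form "must be completed for all adverse events (AE) of Grade 2 or greater severity".

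Numeric limits appear in 5.2.5 (ALT, AST, bilirubin) and 5.2.6 (neutrophils, platelets), where they govern study drug. For grade 2 transaminase or bilirubin "elevations, imatinib must be suspended, and the LFTs monitored weekly". The introduction to 5.2 refers to the toxicities listed after it as AEs.

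Appendix 1 schedules serum chemistry with liver panel, and hematology, at every visit. The hematology footnote reads "Performed locally; to include CBC with differential and platelets". Section 9.2 covers the number, severity and rates of AEs and names no analysis of liver or blood-count values.

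**The concern.** Section 2.2 names hepatic and bone marrow toxicity in the safety objective. Both are largely found by laboratory test: a raised ALT or a low neutrophil count often causes no symptoms. For such a value, observation, questioning and complaint will find nothing, so its place in the endpoint depends on whether the site investigator calls it clinically significant.

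The CTCAE grade does not bypass that step, because the grade 2 rule applies to events that are already AEs. Two sites could see the same value and count it differently. In a trial with few expected events, that can visibly move the reported rate, and the plan has no laboratory-based summary to set beside it.

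**Working it through.** The plan states no figure on this point, so there is none to reproduce. The check has two parts.

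**1. Tracing a symptomless abnormal value through the text**

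- Does 3.3.2 count it? Only if it is an AE.
- Does 8.1.1 make it an AE? Yes, if the investigator judges it clinically significant. Toxicity with clinical signs can enter through the general definition; a value alone cannot.
- Does CTCAE grading (8.1.4) or the grade 2 rule (8.1.1, 8.2) make it an AE? No. They grade and report events already classed as AEs.
- Do the limits in 5.2.5 and 5.2.6 make it an AE? Section 5.2 uses the term AE for these toxicities, but does not say that reaching a limit must be recorded as one.
- Does 9.2 pick it up another way? It has a general method for quantitative variables, but names no liver or blood-count value, and a comparison of means would not show graded toxicity.

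**2. Scale**

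Inputs:

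- Imatinib participants: 66 at 2:1 gives n = 44. Section 9.4 prints the split as 46 + 22, which sums to 68; 46 is used below as a check.
- True event rate p: 1.5.1.6 gives grade 3 transaminase events in 2% to 5% of oncology participants, and 1.5.1.7 gives grade 3 or 4 neutropenia in 5%. These grades lie above the grade 2 reporting floor.
- Share judged clinically significant, s: 0.25 to 1.0. This is an assumption; the documents give no value.

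Formulas: expected number counted = n × p × s. Chance of at least one = 1 − (1 − p × s)^n.

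| p | s | Expected counted (n = 44) | Chance of at least one |
|---|---|---|---|
| 5% | 1.00 | 44 × 0.05 = 2.2 | 1 − 0.95^44 = 0.90 |
| 5% | 0.50 | 1.1 | 0.67 |
| 5% | 0.25 | 0.55 | 1 − 0.9875^44 = 0.43 |
| 2% | 1.00 | 0.88 | 0.59 |
| 2% | 0.25 | 0.22 | 0.20 |

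With n = 46 and p = 5%, the expected count runs from 0.58 to 2.3 and the chance from 0.44 to 0.91, so the choice of n does not matter.

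Scheduled data: weeks 2, 4, 9, 13, 17, 22, 26, 39, 52, 78 and 104 are 11 post-baseline visits, 7 of them by week 26. With full attendance that is 11 × 66 = 726 liver panels and 726 blood counts, of which 7 × 66 = 462 of each fall by week 26. These are upper limits, since 9.4 itself allows for 10% missing at one year.

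**The case against.** Much of the case on the other side stands.

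- **Values that stop drug.** A reader might infer that a transaminase rise which suspends study drug would be missing from the hepatotoxicity rate. The documents do not support that as the expected outcome. Section 5.2 is headed as management of adverse events and calls its listed toxicities AEs. It would be odd for a site to suspend drug for a value and also call it not clinically significant. What remains is that no sentence requires the value to be recorded as an AE.
- **The wording is conventional.** The laboratory clause in 8.1.1 adds a route to AE status and does not use the word only. That is fair, and the clause is ordinary for AE reporting. The point here is narrower: for symptomless values it is the sole stated route into two endpoints.
- **The 10% figure.** A reader might size the problem from section 1.5.1.6, which says "Grade 1 elevations in transaminases occur in up to 10% of treated patients". That would mislead, because the grade 2 floor in 8.2 can remove grade 1 events whatever the investigator decides (the laboratory sentence in 8.1.1 could be read otherwise).
- **Bias between arms.** A reader might infer that imatinib cases would be judged differently from placebo cases. Section 6.2.2 blinds all study personnel except pharmacists. Section 3.6 raises unmasking by side effects, but expects them to be milder and less frequent than in oncology. Differential judgement is speculative.
- **Availability of the data.** The schedule shows that the tests are drawn. It does not show that every value is entered in the eCRF, and hematology is done locally. This has to be confirmed.
- **Replacing the AE rates.** Demoting investigator-declared AEs would be a preference that the text does not compel. An addition is enough.

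**Conclusion.** The point holds as a modest gap in two secondary safety endpoints. Their counts can depend on site judgement for symptomless values, and no planned analysis uses the laboratory values directly. The harm is possible under-counting and variation between sites; the documents do not establish that either will occur.

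At a 5% true rate the count among 44 imatinib participants would lie between 0.55 and 2.2, with a 0.43 to 0.90 chance of recording any case. This rests on an assumed share of 25% to 100% and on oncology rates that 1.5.1.6 and 1.5.1.7 say may partly reflect the underlying disease. For grade 3 values, which would already have met the suspension limits in 5.2.5 or 5.2.6, the upper end of the range is the more plausible. The primary analysis and the sample size are unaffected.

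**What to change.** Keep endpoints 1 and 4 as AE rates. In 3.3.2 and 9.2 add, by arm:

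- the proportion of participants with each worst post-baseline CTCAE 4.0 grade; and
- the shift in grade from baseline,

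for ALT, AST, bilirubin, neutrophils, platelets, hemoglobin and leukocytes, graded by program from all scheduled and unscheduled values.

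Take the grades from CTCAE 4.0, which 8.1.4 adopts, and not from the limits printed in 5.2.6. There, grade 1 platelets run down to 75,000 and grade 2 or greater begins below 50,000, so counts in between have no grade; that text needs to be reconciled separately.

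Confirm that local hematology values and each laboratory's normal ranges are entered in the eCRF.

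The cost is some data entry and programming. No extra sampling is needed. Reported laboratory toxicity may look higher than under AE counts alone. No dosing, discontinuation or AE-reporting rule changes.
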